### **Blood sampling for correlative studies**

- Research blood collection for correlative studies is to be performed at Baseline/Week -2 (anytime pre-treatment), Week 1 (pre-infusion, untimed sample), Week 7 (pre-infusion, untimed sample), and Week 13 (pre-infusion, untimed sample).
- At Baseline, 1 green top tube and 1 red top tube will be collected.
- At Week 1, 1 green top tube and 1 red top tube will be collected.
- At Week 7, 1 green top tube and 1 red top tube will be collected.
- At Week 13, 1 green top tube and 1 red top tube will be collected.
- Refer to the Lab Manual for details on collection, processing and storage.

### **Blood sampling for PK analysis**

[figure not shown]
- Research blood collection for PK analysis is to be performed at the following treatment visits: a) Week -2 at pre-treatment, and at 2 hours and 4 hours post trigriluzole (window  $\pm$  30 minutes), b) Week 1 (untimed sample pre-infusion), and c) Week 7 (untimed sample pre-infusion).
- Approximately 2 mL of blood will be collected in a lavender top EDTA tube, which should be immediately placed on ice.

- Refer to the Lab Appendix for details on collection, processing and shipping.

### **1.9 Interviews, Focus Groups, or Surveys**

N/A

- **Study Design Flow Chart**

Protocol Number: RCINJ# 051707  
PI Name: [name]  
Protocol Title: A Phase I Study to Evaluate the Safety of Trigriluzole (FC-4157/BHV-4157) in Combination with PD-1 Blocking Antibodies

45

RESERVED FOR IRB STAMP  
DO NOT MODIFY THIS SPACE

[figure not shown]

## 1.10 Timetable/Schedule of Events

### Schema

#### Trigriluzole + Nivolumab

#### Trigriluzole + Pembrolizumab

**Trigriluzole + Nivolumab Study Calendar**

	Screening/ Baseline 	Treatment Week									
		Week -2	Week -1	Week 1	Week 3	Week 5	Week 7	Week 9	Q2 weeks (Weeks 11 – 109)	Q4 weeks  (Weeks 13 – 109)	Weeks 13, 25, 37, 49
Scheduling Window (Days):		Within 14 d	±3	±1	±7	±7	±7	±7	±7	±7	±7
Informed Consent	X										
Inclusion/Exclusion Criteria	X										
Demographics and Medical History, including BRAF status	X										
Prior and Concomitant Medication Review	X	X	X	X	X	X	X	X	X	X	X
Assess Baseline Symptoms/Adverse Events and Compliance	X	X	X	X	X	X	X	X	X	X	X
Vital Signs and Weight	X	X	X	X	X	X	X	X	X	X	X
ECOG Performance Status, Physical Examination	X	X		X	X	X	X	X		X	X
Routine Safety Laboratory Studies 	X	X 		X	X	X	X	X		X	X
Serum GGT	X			X			X				X
ECG 		X	X	X			X				X 
Trigriluzole Administration (PO continuous dosing)		X	X	X	X	X	X	X	X	X	X
Nivolumab Administration				X	X	X	X	X	X	X	X
Research Blood Collection for PK 		X		X			X				
Research Blood Collection for correlative science 	X			X			X				X 
Tumor Tissue Collection 	X			X			X				
Tumor Assessment 	X						X				X

Protocol Number: RCINJ# 051707

PI Name: [name]

Protocol Title: A Phase I Study to Evaluate the Safety of Trigriluzole (FC-4157/BHV-4157) in Combination with PD-1 Blocking Antibodies

47

RESERVED FOR IRB STAMP  
DO NOT MODIFY THIS SPACE

Form Version v120116

**RUTGERS | eIRB**  
**APPROVED**

IRB ID: Pro20170000453  
Approval Date: 10/4/2019  
Expiration Date: 4/3/2020

Footnotes

1. Screening evaluations must be performed no more than 28 days prior to registration. The subject must begin study treatment no more than 14 days after registration.
2. Routine safety labs: CBC with Differential, Comprehensive Metabolic Panel, Amylase, Lipase, TSH, Free T4, LDH. Routine safety labs do not need to be repeated on Week -2 if performed in the past 14 days. More frequent labs may be performed as clinically necessary, as determined by treating investigator. WOCBP must have a negative serum beta-HCG pregnancy test prior to the first dose. During study treatment, pregnancy testing may be performed as indicated at the treating physician's discretion.
3. ECG monitoring is to be performed at the following treatment visits: a) at baseline (prior to dose on start date Week -2), and at expected  $C_{max}$  4 hours post trigriluzole (window  $\pm$  30 minutes), b) at steady state on Week -1 and c) at steady state at Week 1 (untimed), d) at steady state at weeks 7, 13, 25, 37, and 49. If trigriluzole has been discontinued, EKG monitoring may be discontinued.
4. Research blood collection for PK analysis is to be performed at the following treatment visits: a) start date (Week -2) at pre-treatment, and at 2 hours and 4 hours post trigriluzole (window  $\pm$  30 minutes), b) Week 1 (untimed sample, pre-infusion), and c) Week 7 (untimed sample, pre-infusion). No PK collections after Week 7.
5. Research blood collection for correlative studies is to be performed at Screening/Week -2 (pre-treatment, untimed), Week 1 (pre-infusion, untimed), Week 7 (pre-infusion, untimed), and Week 13 (pre-infusion, untimed). Baseline research blood and tumor samples may be performed anytime prior to the start of therapy. Ideally, the research blood samples should be collected 3-14 days prior to the fresh tumor biopsy, but it is also acceptable to collect them on the same day. No research bloods after Week 13.
6. Tumor Tissue Collection. Archival tissue (a block or 6-10 unstained slides) will be obtained for all subjects, when available. Research biopsies are optional but strongly encouraged at Baseline/Week -2, and Week 1, and Week 7. No biopsies after Week 7.
7. Tumor Assessment must be performed at Screening, Weeks 7, 13, 25, 37, 49, 61, 73, 85, 97, and 109.
8. Q4 weeks starting from Week 13: Weeks 13, 17, 21, 25, 29, 33, 37, 41, 45, 49, etc.

**Trigriluzole + Pembrolizumab Study Calendar**

	Screening/ Baseline 	Treatment Week							
		Week -2	Week -1	Week 1	Week 4	Week 7	Q3 weeks (Weeks 10 – 109)	Q6 weeks  (Weeks 13 – 109)	Weeks 13, 25, 37, 49
Scheduling Window (Days):		Within 14 d	±3	±1	±7	±7	±7	±7	±7
Informed Consent	X								
Inclusion/Exclusion Criteria	X								
Demographics and Medical History, including BRAF status	X								
Prior and Concomitant Medication Review	X	X	X	X	X	X	X	X	X
Assess Baseline Symptoms/Adverse Events and Compliance	X	X	X	X	X	X	X	X	X
Vital Signs and Weight	X	X	X	X	X	X	X	X	X
ECOG Performance Status, Physical Examination	X	X		X	X	X		X	X
Routine Safety Laboratory Studies 	X	X 		X	X	X		X	X
Serum GGT	X			X		X			X
ECG 		X	X	X		X			X 
Trigriluzole Administration (PO continuous dosing)		X	X	X	X	X	X	X	X
Pembrolizumab Administration				X	X	X	X	X	X
Research Blood Collection for PK 		X		X		X			
Research Blood Collection for correlative science 	X			X		X			X 
Tumor Tissue Collection 	X			X		X			
Tumor Assessment 	X					X			X

Protocol Number: RCINJ# 051707

PI Name: [name]

Protocol Title: A Phase I Study to Evaluate the Safety of Trigriluzole (FC-4157/BHV-4157) in Combination with PD-1 Blocking Antibodies

49

RESERVED FOR IRB STAMP  
DO NOT MODIFY THIS SPACE

Form Version v120116

**RUTGERS | eIRB**  
**APPROVED**

IRB ID: Pro20170000453  
Approval Date: 10/4/2019  
Expiration Date: 4/3/2020

Footnotes

1. Screening evaluations must be performed no more than 28 days prior to registration. The subject must begin study treatment no more than 14 days after registration.
2. Routine safety labs: CBC with Differential, Comprehensive Metabolic Panel, Amylase, Lipase, TSH, Free T4, LDH. Routine safety labs do not need to be repeated on Week -2 if performed in the past 14 days. More frequent labs may be performed as clinically necessary, as determined by treating investigator. WOCBP must have a negative serum beta-HCG pregnancy test prior to the first dose. During study treatment, pregnancy testing may be performed as indicated at the treating physician's discretion.
3. ECG monitoring is to be performed at the following treatment visits: a) at baseline (prior to dose on start date Week -2), and at expected Cmax 4 hours post trigriluzole (window  $\pm$  30 minutes), b) at steady state on Week -1 and c) at steady state at Week 1 (untimed), and d) at steady state at weeks 7, 13, 25, 37, and 49. If trigriluzole has been discontinued, EKG monitoring may be discontinued.
4. Research blood collection for PK analysis is to be performed at the following treatment visits: a) start date (Week -2) at pre-treatment, and at 2 hours and 4 hours post trigriluzole (window  $\pm$  30 minutes), b) Week 1 (untimed sample, pre-infusion), and c) Week 7 (untimed sample, pre-infusion). No PK collections after Week 7.
5. Research blood collection for correlative studies is to be performed at Screening/Week -2 (pre-treatment, untimed), Week 1 (pre-infusion, untimed), Week 7 (pre-infusion, untimed), and Week 13 (pre-infusion, untimed). Baseline research blood and tumor samples may be performed anytime prior to the start of therapy. Ideally, the research blood samples should be collected 3-14 days prior to the fresh tumor biopsy, but it is also acceptable to collect them on the same day. No research bloods after Week 13.
6. Tumor Tissue Collection. Archival tissue (a block or 6-10 unstained slides) will be obtained for all subjects, when available. Research biopsies are optional but strongly encouraged at Baseline/Week-2, Week 1, and Week 7. No biopsies after Week 7.
7. Tumor Assessment must be performed at Screening, Weeks 7, 13, 25, 37, 49, 61, 73, 85, 97, and 109.
8. Q6 weeks: Weeks 13, 19, 25, 31, 37, 43, and 49, etc.

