**RUTGERS | eIRB**  
**APPROVED**

IRB ID: Pro20170000453  
Approval Date: 10/4/2019  
Expiration Date: 4/3/2020

The study design consisted of the administration of single doses of trigriluzole (sequential cohorts with 17.5, 35, 70, 140 and 200 mg, with the last cohort undergoing repeat dosing under conditions of a high-fat meal) and 5 days of multiple dose (sequential cohorts administered doses of 17.5, 35, 70, and 100 mg BID followed by 200 mg qD). To date of this writing, preliminary results are available (single doses up to 200 mg fasted and fed; multiple doses of 100 mg BID mg daily). Overall, single doses up to 200 mg and multiple doses up to 200 mg daily have been well tolerated without evidence of novel, clinically significant safety signals or lab abnormalities. In addition, PK suggests minimal accumulation with daily dosing.

Under single dose fasting conditions, riluzole concentrations at 24 hours after dosing average under 5% of peak concentrations. PK appears linear. No food effect was observed based on AUC; however, Cmax concentrations were reduced for both trigriluzole and riluzole. A single dose of 140 mg trigriluzole yields exposures (e.g., AUCinf 1,014.7 ng\*h/mL) that are expected to be similar to that achieved in clinical trials using riluzole tablets at 50 mg BID (e.g., approximately 1254 ng\*h/mL, based on Chandu et al 2010), a dose which was previously studied in ataxia (Romano et al 2015; Ristori et al 2010).

Performance in healthy volunteers has been similar to what has been observed in preclinical species, insofar as the concentrations of trigriluzole have been negligible compared to active metabolite and time to peak concentration of the active metabolite have been delayed. That is, the AUC of the active metabolite riluzole is shown to be over 350-fold greater than trigriluzole

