#### **1.4.6 Pharmacokinetics and Dose Selection Rationale**

Clinical pharmacokinetics is pending and will be available via an amendment to the IB. The starting dose of 140 mg of trigriluzole is the molar equivalent of 70 mg riluzole, which is below the well-tolerated riluzole dose of 100 mg per day that has been administered chronically to patients with ALS and SCA. This dose of trigriluzole is selected to provide riluzole exposure that is comparable to that achieved in the two positive randomized controlled trials of riluzole in SCA.

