### **1.7.5 TREATMENT PLAN**

#### **1.7.5.1 Study Agents**

##### **Trigriluzole**

All patients will receive trigriluzole, which will be self-administered as continuous oral daily to BID dosing, depending on the dosing cohort (see Table 3). Subjects will begin therapy with the prescribed dose of trigriluzole for a run-in period of 14 days. After the lead-in period, subjects will continue trigriluzole and begin therapy with pembrolizumab or nivolumab. The first dose of trigriluzole will be administered in the clinic. The patient will have PK and EKG done after the first dose.

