### **1.7.6 Treatment Administration**

#### **Trigriluzole Administration**

Trigriluzole will be self-administered by the patient. Trigriluzole will be first administered in the clinic setting. Trigriluzole can be taken without regards to meals (on a full stomach or an empty stomach). Morning or evening administration is acceptable for once daily dosing. No weight-based dosing calculation is necessary as trigriluzole is administered using flat dosing.

**Lead-in period.** Subjects will begin therapy with continuous oral dosing of trigriluzole for a lead-in period of 14 days (Week -2, Day -14 to Week -1, Day -1). Day -1 is followed by Day 1 (There is no Day 0 or Week 0).

**Combination treatment.** At the start of Week 1, subjects will continue oral dosing of trigriluzole and begin therapy with PD-1 inhibitor. On the days of IV treatment visits, there is no window for administration of trigriluzole with respect to the PD-1 inhibitor.

**Compliance/adherence assessment.** Subjects will be *strongly encouraged* to use the Pill Diaries that are provided by the study. If a patient reports compliance <80% of days, they should be re-educated by the research nurse and/or treating investigator on instructions for dosing trigriluzole at home.

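### The only clock-timed post-dose ECG is set at 4 h and labelled the expected Cmax, but the protocol's own PK tables put the riluzole peak at about 1.3 to 2.8 h

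*Combined protocol and SAP*

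**What the plan says.** Footnote 3 is worded alike in the nivolumab and pembrolizumab calendars (section 1.10). On the first dosing day it asks for an ECG before the dose and a second one "at expected Cmax 4 hours post trigriluzole", ±30 minutes. The remaining on-treatment ECGs are "at steady state on Week -1 and c) at steady state at Week 1 (untimed"), and then at Weeks 7, 13, 25, 37 and 49. None of these has a time relative to the dose.

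Section 1.7.5.1 ties the timed tracing to the first in-clinic dose: "The patient will have PK and EKG done after the first dose". Section 1.8 schedules PK samples that day before the dose "and at 2 hours and 4 hours post trigriluzole", so the 4 h ECG coincides with a PK sample and the 2 h sample has no ECG beside it. On food, section 1.7.6 states: "Trigriluzole can be taken without regards to meals".

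The evidence on timing is in section 1.4.3, Tables 1 and 2, from healthy volunteers, described there as preliminary. Table 1 gives a riluzole Tmax of 1.53 h (range 1.0–2.5 h) at 140 mg.

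**The concern.** An ECG labelled as taken at Cmax is meant to look for a cardiac effect when exposure is greatest. If the peak has usually passed, a normal tracing gives less reassurance than its label implies. Because no other on-treatment ECG is timed, nothing later in the schedule reliably makes up for it.

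Safety is this trial's primary objective, and Cohort 4 gives 280 mg per administration, more than any single dose in the PK tables. What is at stake is the quality of first-dose ECG monitoring. The DLT definition, the escalation rules, the MTD and the sample size do not depend on it.

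**Working it through.** **1. Tmax against the ECG window.** The footnote gives 4 h ± 0.5 h = 3.5–4.5 h. Riluzole Tmax in section 1.4.3:

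| Dose group | n | Central Tmax (h) | Range (h) |
|---|---|---|---|
| Single 17.5 mg | 6 | 1.67 | 1.33–3.0 |
| Single 35 mg | 5 | 2.03 | 1.33–3.0 |
| Single 70 mg | 5 | 2.07 | 1.33–3.0 |
| Single 140 mg | 6 | 1.53 | 1.0–2.5 |
| Single 200 mg fasted | 6 | 2.64 | 1.67–4.0 |
| Single 200 mg fed | 6 | 2.83 | 2.0–6.0 |
| 17.5 mg BID, Day 1 / Day 5 | 6 | 1.45 / 1.67 | 1.0–1.67 / 1.0–3.0 |
| 35 mg BID, Day 1 / Day 5 | 6 | 1.44 / 1.31 | 0.67–2.0 / 0.67–2.5 |
| 70 mg BID, Day 1 / Day 5 | 6 | 1.33 / 1.58 | 1.0–1.67 / 1.0–2.5 |
| 100 mg BID, Day 1 / Day 5 | 6 | 1.72 / 1.67 | 0.67–2.5 / 1.0–4.0 |

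The 14 central values span 1.31–2.83 h, and none is in the window. Individual ranges reach 3.5 h or later in 3 of 14 cells: 200 mg fasted, 200 mg fed and 100 mg BID on Day 5. Using the parent drug instead does not help the label; its central Tmax is 0.38–1.58 h.

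**2. The dose that the ECG follows.** By Table 3, each administration is 140 mg in Cohorts -1, 1 and 2. The morning dose in Cohort 3 is also 140 mg, and I assume that it is the one given in clinic. At 140 mg the latest peak was 2.5 h, which is 3.5 − 2.5 = 1.0 h before the window opens. Taking all first-dose groups at 140 mg or below: 6 + 5 + 5 + 6 = 22 single-dose volunteers and 4 × 6 = 24 on Day 1 of multiple dosing, 46 in all. Their latest peak was 3.0 h, assuming that every tabulated volunteer contributed a Tmax.

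**3. How far past the peak.** The inputs are Table 1 Cmax, Tmax (tm) and AUCinf; at 140 mg these are 210.2 ng/mL, 1.53 h and 1,014.7 ng·h/mL, so AUC/Cmax = 4.83 h. The curve shape is an assumption, so four were tried.

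- (A) One compartment, first-order absorption: solve exp(ke·tm)/ke = AUC/Cmax for ke, then obtain ka from tm. At 140 mg, ke = 0.359 and ka = 1.078 per hour. A solution needs AUC/(Cmax·tm) of at least 2.72, so there is none at 70 mg (2.62) or 200 mg fasted (2.18).
- (B) Linear rise, exponential fall: k = 1/(AUC/Cmax − tm/2) = 1/(4.83 − 0.765) = 0.246 per hour, so C(4 h)/Cmax = exp(−0.246 × 2.47) = 0.54.
- (C) Gamma-shaped curve matched to AUC/Cmax.
- (D) Decline fixed by the section 1.4.3 statement that "riluzole concentrations at 24 hours after dosing average under 5% of peak concentrations", set here at exactly 5%. In the log-linear form, k = ln 20/(24 − 1.53) = 0.133 per hour and C(4 h)/Cmax = exp(−0.133 × 2.47) = 0.72. A one-compartment version gives 0.77, but it implies 1.87 times the tabulated AUC.

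Fraction of peak concentration:

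| Dose | Time | A | B | C | D |
|---|---|---|---|---|---|
| 140 mg | 2 h | 0.97 | 0.89 | 0.97 | 0.94–0.98 |
| 140 mg | 4 h | 0.58 | 0.54 | 0.60 | 0.72–0.77 |
| 200 mg fasted | 2 h | – | 0.76 | 0.95 | 0.76–0.97 |
| 200 mg fasted | 4 h | – | 0.74 | 0.86 | 0.83–0.93 |
| 200 mg fed | 2 h | 0.95 | 0.71 | 0.95 | 0.71–0.95 |
| 200 mg fed | 4 h | 0.94 | 0.85 | 0.94 | 0.85–0.95 |

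At 140 mg the 4 h level is 54–77% of peak (54–60% for the curves that reproduce the AUC), against 89–98% at 2 h. At 200 mg the 4 h shortfall is smaller, about 7–26% fasted and 5–16% fed, and 2 h is not clearly better. There is nothing to compute for 280 mg.

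**The case against.** The evidence at a dose used in this trial is thin. Of the 46 volunteers counted, 40 took 17.5–100 mg per dose and only 6 took 140 mg, apparently fasted. At 200 mg, the nearest tested dose above, peaks were seen as late as 4.0 h fasted and 6.0 h fed, and subjects may take the drug with food. The proposed 2 h window (1.5–2.5 h) contains the 140 mg central Tmax by only 0.03 h and misses both 200 mg central values. The concentration ratios are modelled from group summaries. The PK is preliminary, and the investigator's brochure, which might support 4 h, is not among these documents. No ECG endpoint or analysis is specified, and the 2 h and 4 h PK samples show exposure on either side.

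Much of this stands as a limit. A 4 h peak cannot be excluded for a late absorber, for fed dosing or for 280 mg, and the percentages are only illustrative. It does not rescue the label. The footnote says expected, and no group's central value is near 4 h. Food moved the central Tmax at 200 mg only from 2.64 to 2.83 h, so a fed 140 mg peak at 4 h is not the expected case, though it is untested. A PK sample at 4 h reports exposure at that moment; it does not supply an ECG at the peak. The point about 2 h at higher doses is fair and argues for keeping a 4 h tracing there.

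**Conclusion.** The concern holds. The 4 h time is not the expected Cmax on any PK evidence in the protocol. For a 140 mg first dose the tracing would typically fall after the peak, at roughly 54–77% of the maximum concentration. The mismatch itself rests only on the tabulated Tmax values; the percentages also depend on the assumed curve and on preliminary summaries from 5–6 volunteers per group. The tables do not say whether the central Tmax is a mean or a median.

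The consequence is limited to first-dose ECG monitoring, and the documents report no cardiac signal. The correction should still be made, because this is the only on-treatment ECG with a time after dosing.

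**What to change.** In footnote 3 of both calendars, move the timed Week -2 ECG to 2 h (±30 min) after the first dose, paired with the PK sample already drawn then, and delete the reference to expected Cmax at 4 h.

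Where the first single dose is 280 mg (Cohort 4, and the pembrolizumab cohort if that dose is carried forward), keep a second ECG at 4 h without the Cmax label. Keeping it for everyone is a reasonable option given that food is allowed.

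The cost is a wording change in two footnotes. For 140 mg first doses it adds no procedure. Where the 4 h tracing is kept, it adds one ECG per subject at a visit where the 4 h PK sample already holds the subject in clinic.

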**Study Calendar: Follow-Up (Nivolumab and Pembrolizumab cohorts)**

Protocol Number: RCINJ# 051707

PI Name: [name]

Protocol Title: A Phase I Study to Evaluate the Safety of Trigriluzole (FC-4157/BHV-4157) in Combination with PD-1 Blocking Antibodies

50

RESERVED FOR IRB STAMP  
DO NOT MODIFY THIS SPACE

 **RUTGERS | eIRB**  
APPROVED  
Form Version v120116

IRB ID: Pro20170000453  
Approval Date: 10/4/2019  
Expiration Date: 4/3/2020

	Off treatment but on study Q6 weeks	Off treatment but on study Q12 weeks	Safety Follow-up (12 weeks after last dose of rx)	Long-Term Follow-up Q12 weeks
Scheduling Window (Days):	±14	±14	±28	± 28
Prior and Concomitant Medication Review	X	X	X	
Assess Baseline Symptoms/Adverse Events and Compliance	X	X	X	
Vital Signs and Weight, ECOG Performance Status, Physical Examination	X	X	X	
Routine Safety Laboratory Studies	X	X	X	
Tumor Assessment 		X	X	
Post-study survival status, and receipt of subsequent anticancer therapy				X

Footnotes

1. If a subject has discontinued active treatment due to reasons other than PD (such as toxicity or patient preference), the subject will continue to have CT scans and follow-up visits to monitor them until Week 49.
2. Tumor Assessment must be performed at the same Weeks as subjects who remain on active treatment (Week 7, Week 13, and then Q12 weeks up until Week 49).
3. Safety follow-up visit will occur at Week 61 for subjects who complete all treatment (Week 49), but it will occur prior to Week 61 if active treatment is discontinued early for PD or other reasons.
4. Long-term Follow-up. Subjects will remain in the follow up phase of the trial for up to 3 years until the start of another therapy, withdrawal of consent or death.

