### **1.3.5 Active phase, combination treatment**

After Week 2, regular study visits will occur in the outpatient clinic at an interval of 14 or 21 days (depending on whether treatment includes nivolumab or pembrolizumab) as per the Study Calendar.

Subjects will receive treatment up to 109 weeks. Subjects may elect to discontinue therapy at any time for any reason. Subjects will remain on the active treatment phase of the study until confirmed disease progression, unacceptable toxicity, or withdrawal of consent, up to a maximum treatment duration of 109 weeks. Once the subject discontinues active treatment, the subject will enter the follow-up phase.

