#### **Timing of Assessments**

For the purposes of this study, patients should be evaluated at baseline and then reevaluated for response at Week 7, Week 13, and then every 12 weeks thereafter per the Study Calendar. Confirmatory scans should be obtained not less than 4 weeks following

initial documentation of objective response or progressive disease (PD). If a subject has discontinued active treatment due to reasons other than PD, the subject will continue to have CT scans Q12 weeks until Week 49 (window can be widened to  $\pm 28$  days).

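### Footnote 3 of the Follow-Up calendar dates the safety visit as if treatment ended at Week 49, which conflicts with its own column header for later last doses

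*Combined protocol and SAP*

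**What the plan says.** **Treatment length.** Section 1.3.5 keeps subjects on treatment "up to a maximum treatment duration of 109 weeks"; Sections 1.3.2 and 1.7.13 give the same maximum. Both treatment calendars in Section 1.10 run to Week 109, and footnote 7 of each states: "Tumor Assessment must be performed at Screening, Weeks 7, 13, 25, 37, 49, 61, 73, 85, 97, and 109".

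**Safety visit.** In the Follow-Up calendar the column is headed "Safety Follow-up (12 weeks after last dose of rx", with a window of ±28 days. Footnote 3 to that column reads "Safety follow-up visit will occur at Week 61 for subjects who complete all treatment (Week 49" and adds that "it will occur prior to Week 61 if active treatment is discontinued early for PD or other reasons".

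**Off-treatment visits and scans after a stop for reasons other than progression.** Footnote 1 says "the subject will continue to have CT scans and follow-up visits to monitor them until Week 49". Footnote 2 says "Tumor Assessment must be performed at the same Weeks as subjects who remain on active treatment", but its parenthesis ends the list at Week 49. Section 1.7.12 (Timing of Assessments) says "the subject will continue to have CT scans Q12 weeks until Week 49". Section 1.3.6 limits these procedures to one year counted from the start of treatment, and describes the active phase as lasting one year.

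**Afterwards.** Long-term follow-up (Section 1.3.7) collects survival status and receipt of further therapy by contact every 12 weeks, with no examination or scan.

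**The concern.** Footnote 3 and the one-year wording in Section 1.3.6 fit a 49-week treatment period, not the 109 weeks allowed elsewhere. A site that follows the footnote for a subject treated beyond Week 61 would be sent to a post-treatment visit dated before treatment ended.

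The visit matters because, for a subject who stops after Week 49, it is the only scheduled post-treatment symptom review, examination, laboratory check and tumor assessment. Section 1.7.7 notes that PD-1 inhibitor events can appear several months after the last dose. The date conflict applies to stops for progression as well as for other reasons.

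The limit on off-treatment imaging raises a second, smaller question. Section 1.7.12 ends duration of response at objectively documented progression. After a late stop without progression, that date would rest on one scheduled scan or on unscheduled imaging.

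**Working it through.** This is calendar arithmetic. Inputs: the header rule (last dose L plus 12 weeks, ±4 weeks), footnote 3 (Week 61, with completion at Week 49), maximum treatment of 109 weeks, and the footnote 7 scan weeks.

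**Reproducing the plan's figure.** 49 + 12 = 61. Footnote 3 is therefore the header rule worked out for a last dose at Week 49.

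**Applying the header rule to later last doses.** The header date is L + 12 and its window is L + 8 to L + 16. Footnote 3 allows Week 61 at the latest, or Weeks 57 to 65 if ±28 days is applied to that date too.

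| Last dose (week) | Header date | Header window | Against footnote 3 |
|---|---|---|---|
| 49 | 61 | 57–65 | Same date |
| 50 | 62 | 58–66 | Dates differ; Week 61 is inside the window |
| 53 | 65 | 61–69 | Week 61 just inside |
| 54 | 66 | 62–70 | Week 61 outside the header window |
| 57 | 69 | 65–73 | Two windows meet only at Week 65 |
| 58 | 70 | 66–74 | No overlap even with ±28 days on both |
| 61 | 73 | 69–77 | Footnote date falls on the last dose |
| 109 | 121 | 117–125 | Footnote date is 109 − 61 = 48 weeks before the last dose |

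The thresholds follow from L + 8 > 61, which gives L ≥ 54, and L + 8 > 65, which gives L ≥ 58. There are 60 possible last-dose weeks after Week 49 (50 to 109). Of these, 56 (54 to 109) fail on the first reading and 52 (58 to 109) on the second. These are counts of calendar weeks, not of subjects.

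**Off-treatment scans.** One year from Day −14 falls in Week 51: (365 − 14)/7 = 50.1 completed weeks. The one-year limit in Section 1.3.6 and the Week 49 limit therefore nearly coincide. For a non-progression stop after Week 49 no recurring off-treatment scan remains, so the scheduled number is 0 + 1 (safety visit) = 1. Footnote 2 is attached to the whole tumor-assessment row, which includes the safety-visit column. Read literally, its Week 49 limit would remove even that scan.

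On-treatment scan weeks after Week 49 are 61, 73, 85, 97 and 109. If off-treatment scans followed them, the number after stopping would be 5 for a stop at Week 50, 4 at Week 70, 2 at Week 86 and 1 at Week 98. One of these could double as the safety-visit scan. Week 109 is used here only as a yardstick; no text in the plan sets it for subjects off treatment.

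**The case against.** The header alone gives a workable rule for every last dose, and footnote 3 can be seen as a leftover worked example. Since a post-treatment visit cannot precede the end of treatment, a sensible site would follow the header. That is a fair prediction of practice, but the footnote is written as a rule, covers early stops too, and should not need to be overridden.

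Routine adverse event and SAE collection ends 30 days after the last dose (Section 1.7.11), whereas the correctly dated visit falls 8 to 16 weeks after it. Moving the visit therefore does not change event capture within the defined period. This stands; the gain is in a clear date for the later check.

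The strongest objection concerns imaging. A reader might infer that the Week 49 limit is an error and that scans must run to Week 109. The documents do not support that. The limit appears consistently in four places (footnotes 1 and 2, Section 1.7.12 and Section 1.3.6), and a one-year cap is a coherent choice for a phase I trial of 12 to 27 subjects. Counted from the start of treatment, late stoppers have no fewer scheduled scans than early stoppers. Extension to Week 109 would mostly add scans for early stoppers, who are not the group with the gap. Nor is a single scan an absolute limit: Section 1.7.12 calls for a confirmatory scan once response or progression is initially documented.

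**Conclusion.** Footnote 3 is wrong as written for treatment beyond Week 49. The nominal dates conflict for any last dose after Week 49 and cannot be reconciled from Week 58 on the most generous use of the window (Week 54 if the window is applied to the header only). The footnote becomes impossible as a post-treatment visit after Week 61. This rests only on the plan's own dates, counted in whole weeks.

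The imaging limit is a point to confirm, not an established error. It looks like a leftover, given the one-year description of the active phase and footnote 2's clash with scan weeks that run to Week 109, but it could be deliberate. A reader might also infer that the efficacy results or the dose decision are compromised. The documents do not support that: PFS and duration of response are secondary and descriptive (Section 6.1), and MTD/RP2D and overall survival are unaffected. The number of subjects who would stop without progression after Week 49 is not given and may be small.

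**What to change.** 1. Reword footnote 3 so that the safety visit falls 12 weeks (±28 days) after each subject's actual last dose. State that its tumor assessment is kept whatever the study week.
2. Correct the description of the active phase as one year in Section 1.3.6. Decide the restart clause in that section separately, because lengthening its one-year period would widen eligibility for re-treatment.
3. Confirm whether the Week 49/one-year limit on off-treatment visits and scans is intended now that treatment may run to Week 109. If so, state it as a cap and remove footnote 2's claim that the scan weeks match those of subjects on treatment.

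Items 1 to 3 are wording changes and cost almost nothing beyond an amendment. Item 1 gives a Week 109 completer a correctly timed visit at Week 121.

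Extending off-treatment scans is optional and is a real change in procedures. It would add up to 5 visits with scans every 12 weeks (Weeks 61, 73, 85, 97, 109) for each progression-free subject off treatment. If the 6-weekly column also ran on, it would add up to 10 visits (every 6 weeks from Week 55 to Week 109), 5 of them with scans. The return is better-dated progression for two descriptive endpoints.
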